#### A. Safety:

The following safety data will be collected and assessed during the study:

- 1) Incidence and severity of adverse events
- 2) Laboratory evaluations
- 3) Home glucometer measurements for diabetic participants
- 4) Home blood pressure measurements for hypertensive participants
- 5) Home daily weight measurements for patients with congestive heart failure or diuretic use

Safety data will be collected and assessed using the following methods:

- 1) Each participant will receive a paper copy and an emailed daily diary requesting information on symptoms (including duration and severity), vitals, and medication compliance. Participants who are unable to respond to emails will be asked to directly record this data into the provided paper study daily diary and then will be contacted daily to report this information to the study coordinator. All email exchanges among study personnel will be conducted within the UC intranet secure system. All communications with patients will be through virtual appointments using UC secure systems, UC San Diego encrypted emails or with password-protected study documents.
- 2) Study coordinators will collect and enter all safety data. All serious adverse events (SAEs) will, per UCSD IRB guidelines, be reported to the IRB and DSMB within 3 business days of learning of the event. Any adverse events, as well as any escalation of care, including urgent care, emergency room, or hospitalization, will be reported to the study team after appropriate medical care has been received, via a dedicated phone number or email address that is specific for urgent matters.
- 3) The UCSD site will implement a Data and Safety Monitoring Board (DSMB) to review data safety and monitoring as part of their responsibilities. The DSMB will include two senior researchers and a consumer representative. They will have conference calls bi-weekly (or more frequently, if needed).
- 4) The study biostatistician will send a tabulated symptom and adverse event report daily to all sites and to the study PI and weekly to the study DSMB and IRB.
- 5) The safety of the study medication will also be assessed through laboratory data collection at baseline, and at either the end of the treatments following end of quarantine (for non-hospitalized patients) or as part of hospital admission labs (for patients requiring hospitalization)
  - a. Basic Metabolic Panel
  - b. Complete Blood Count with Differential
  - c. Liver Function Testing

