#### **(1) Screening/Baseline:**

##### **Screening:**

The following laboratory tests will be conducted and reviewed prior to study initiation to confirm that liver and renal failure (exclusion criteria) are not present:

- Basic Metabolic Panel
- Liver Function Testing
- Prothrombin Time and Partial Thromboplastin Time

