required methodological modifications. The safety data will be summarized by treatment group and site. Adverse events will be tabulated. These will include the number of participants for whom the event occurred, the rate of occurrence, and the severity and relationship of adverse events to study treatment. Safety data will be analyzed using ANOVAs for continuous variables and Chi-square analyses for dichotomous variables at each time point. Wilcoxon-Mann-Whitney rank-sum test will be used to analyze treatment arm versus control arm across study visits and sites. We anticipate using non-parametric tests because the majority of the outcome measures used in our research may not be normally distributed. The Kruskal-Wallis test will be used to determine whether samples from each of the two arms originated from the same distribution. Since nonparametric tests are based on complete data and ignore missing follow-up data, general linear mixed regression modeling (Gibbons et al, 1988; Hedeker et al, 199; Laird et al, 1982) will be used to confirm the results of the nonparametric tests. The two arms will be compared over time with a focus on the treatment by Time interaction effect. Mixed regression modeling offers robust handling of missing data (Little, 1996) with an assumption that the data is missing at random. This method allows the inclusion of subjects with missing data or those who were terminated early in the study, without relying on data imputation procedures. This method provides an estimate of the individual variability around the population trend, the variability of the individual intercepts (baseline values) and slopes (changes across time), and the correlation between them. Co-variance structure will be chosen based on Akaike's Information Criterion (AIC). Random group level treatment effects will also be evaluated for importance based on the model AIC. Denominator degrees of freedom will be calculated using the Kenward-Roger small sample correction.

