#### **Exclusion Criteria**

1. Any of the following symptoms which, according to the CDC, require hospitalization:
  - a. Trouble breathing
  - b. Persistent pain or pressure in the chest
  - c. New confusion or inability to arouse
  - d. Bluish lips or face
2. Current use of investigational agents to prevent or treat COVID-19
3. Known liver disease (ALT/AST >3x ULN or diagnosis of cirrhosis)
4. Known renal disease (eGFR < 60 ml/min) or acute nephritis.
5. Uncontrolled hypertension (SBP>140 or DBP>90 while on medications)
6. Pregnant or breastfeeding women

Sub-study 1b mQFPD vs. placebo:

66 total patients (N=27 in each of two study arms: mQFPD and placebo plus an additional 20% per arm to guard against dropout) who have tested positive for COVID-19 and are mildly-to-moderately symptomatic will be included in the study.

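### No per-participant laboratory abnormality outcome is defined, so the planned mean and rank comparisons could miss a few severe cases, and the adverse event table is not assured to catch them

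*Combined protocol and SAP*

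**What the plan says.** Safety is a primary objective of sub-studies 1a and 1b and part of the primary objective of 1c. In section 6, the list of safety data for 1a and 1b includes "2) Laboratory evaluations". Under Clinical Laboratory Measurements, 1a and 1b have a metabolic panel, liver tests, blood count and clotting tests before treatment and at Day 14. Sub-study 1c has a metabolic panel and liver tests at baseline and Day 14.

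The Statistical Methods section gives the analysis:

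- "Safety data will be analyzed using ANOVAs for continuous variables and Chi-square analyses for dichotomous variables at each time point".
- Beside this, a comparison of ranks is planned: "Wilcoxon-Mann-Whitney rank-sum test will be used to analyze treatment arm versus control arm across study visits and sites".
- For the mixed model, "The two arms will be compared over time with a focus on the treatment by Time interaction effect".
- Descriptively, "The safety data will be summarized by treatment group and site". Adverse events are tabulated by number of participants and rate, along with "the severity and relationship of adverse events to study treatment".

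Laboratory limits appear only at entry. Screening tests are reviewed "to confirm that liver and renal failure (exclusion criteria) are not present". The 1a and 1b exclusion criteria give the liver limit as "Known liver disease (ALT/AST >3x ULN or diagnosis of cirrhosis", and also an eGFR limit of 60 ml/min. The 1c exclusion criteria name liver and renal disease without a cutoff.

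**The concern.** Organ injury from a study product often shows as a few very abnormal individuals rather than a shift of the whole arm. One to three extreme values inflate the error variance of an ANOVA and barely move a rank sum. The chi-square provision could help, but no dichotomous laboratory variable is defined for it to act on. The ANOVA at each time point also has no baseline term, although a pre-treatment value is collected for these panels.

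This matters because Phase 2 is to follow once safety and feasibility are established (section 5). Section 7 knows of no human trial of Fo, and section 14 relies on Phase 1 to detect adverse effects of FoTv. For mQFPD, section 14 discusses aristolochic acid and the replacement of one herb because of possible liver injury. Individual organ injury is thus an event the protocol itself foresees.

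**Working it through.** **The plan's own figure.** The sample size section has 27 per arm plus 20%: 27 × 1.2 = 32.4, rounded up to 33 per arm, 66 in total. This reproduces. No power, SD or event rate is given for any laboratory outcome, so there is no stated detection figure to check.

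**Inputs from the documents.** Two-sided tests at 0.05; 1:1 allocation; 27 evaluable or 33 enrolled per arm (1a, 1b); 133 per arm (1c).

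**Assumptions, not from the documents.** ALT is log-normal with median 25, log-SD 0.5 and ULN 40. A number k of treated participants lie around 5 or 10 × ULN (log-SD 0.2 about that level), and none on placebo. There were 1,500 simulated trials per row.

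Percentage of trials with p≤0.05:

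| Per arm | k | × ULN | ANOVA, raw | ANOVA, log | Rank-sum |
|---|---|---|---|---|---|
| 27 | 2 | 5 | 4.7 | 10.1 | 6.7 |
| 27 | 2 | 10 | 0.5 | 9.1 | 5.7 |
| 27 | 3 | 5 | 16.8 | 16.0 | 8.7 |
| 27 | 3 | 10 | 7.7 | 18.6 | 8.2 |
| 33 | 2 | 5 | 5.9 | 7.9 | 5.7 |
| 33 | 2 | 10 | 0.7 | 9.8 | 5.7 |
| 33 | 3 | 5 | 17.7 | 15.4 | 9.5 |
| 33 | 3 | 10 | 8.3 | 16.0 | 6.9 |
| 33 | 5 | 5 | 77.8 | 39.3 | 15.5 |
| 33 | 5 | 10 | 97.9 | 47.9 | 14.5 |
| 133 | 3 | 5 | 16.1 | 8.5 | 5.2 |
| 133 | 3 | 10 | 15.1 | 10.7 | 5.3 |

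With two or three affected, raw ANOVA becomes less sensitive at 27–33 per arm as the values grow more extreme. The top of the raw-scale range (three at 5 × ULN) depends on the assumed spread. It lay between 14% and about 20% over log-SDs of 0.40 to 0.50 and spreads of 0 to 0.2 about the affected level. The conclusion does not change.

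**Mixed model.** With two laboratory time points, treatment by time is in effect a comparison of change from baseline. Assuming a log-SD of 0.45, a baseline correlation of 0.5–0.7 and 5–10 × ULN at 27–33 per arm, it reaches p≤0.05 in 0–4% of trials with two affected (log scale 8–9%). With three affected the figures are 3–16% (log scale 15–20%).

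**What counting shows.**

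- 3/33 against 0/33 is 9.1% (exact 95% CI for that arm 1.9% to 24.3%) against 0%.
- The Newcombe 95% interval for the difference is −3% to +24%. Fisher p = 0.24; uncorrected chi-square p = 0.076.
- With 0/33, the one-sided 95% upper bound is 1 − 0.05^(1/33) = 8.7%.

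**Baseline adjustment.** Let ρ be the correlation of baseline with follow-up.

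- Against ANOVA on the follow-up value, ANCOVA multiplies the variance by 1 − ρ²: 0.75 at ρ = 0.5 and 0.51 at ρ = 0.7.
- Against a change-score comparison, whose factor is 2(1 − ρ), the ratio is (1 + ρ)/2: 0.75 and 0.85. The gain over the mixed model is therefore smaller at ρ = 0.7.

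**The case against.** A reader might infer that laboratory safety is judged only by these tests, and that severe cases would be reported as no difference between arms. The documents do not support that:

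- The same section plans a mixed model, which uses baseline values, as well as summaries by arm and an adverse event table by participant and severity.
- Under Adverse Events in section 9, end-of-treatment laboratory tests are one of three monitoring formats, and severity or grade goes on the case report form.
- Section 12 has hospital admission laboratory values compared with baseline, and a DSMB meets every two weeks.

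A participant at 10 × ULN therefore has a planned route into the report. What remains is that no grading scale is named and no rule turns a laboratory value into an adverse event, so the route is open but not assured.

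Two further points stand. The plan allows log transformation, so the near-zero raw-scale figures are the worst case; the log-scale figures are still low. The problem is also confined to a few cases: with five of 33 affected, raw ANOVA usually rejects.

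Finally, a test on threshold counts would also be non-significant at 3 against 0. That is correct, so the case for counts rests on what they show and not on power. The plan's own caution about small samples does not supply those counts.

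**Conclusion.** The point holds as a gap in specification that should be fixed; it does not invalidate the study. No laboratory threshold, grade, shift table or abnormality count is defined as an outcome. With two or three severely affected participants at 27–33 per arm, the planned tests would be non-significant in roughly four trials out of five or more: raw ANOVA significant in about 0–18%, rank tests in 6–10%, log-scale ANOVA in 8–19%. Those percentages rest on assumed ALT values. Over 5–10 × ULN and the spreads tried, the message is the same.

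The claim reaches no further than this: a few severe cases could be reported as no significant laboratory difference, and whether the adverse event table also shows them depends on a rule the protocol does not contain.

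**What to change.** In the Statistical Methods section, make the main laboratory safety display, by arm:

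1. A baseline-to-end-of-treatment shift table for each safety analyte actually drawn. In 1c that means the metabolic panel and liver tests only.
2. The number and percentage who newly cross a prespecified abnormality limit, with the risk difference and an exact 95% CI. Use one named standard grading scale for all sub-studies, because the protocol's numerical limits cover only ALT/AST and eGFR, and only for entry to 1a and 1b.

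State which graded values are entered as adverse events for the analysis table. This is a reporting rule and does not touch clinical management.

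Keep the mean comparison as support only, as ANCOVA on the baseline value, on the log scale where the analyte is skewed. Say in the text that these displays are read as counts with intervals, and that a non-significant test is not evidence of laboratory safety.

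The cost is a paragraph of wording and a few more tables. No new data, visit or participant is needed.

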#### B. Feasibility:

The following feasibility data will be collected and assessed :

- 1) Recruitment:
  - a. Recruitment sites (number, location, and method of their selection)
  - b. Factors influencing recruitment rate
  - c. Methods used for subject recruitment
  - d. Number of subjects:
    - I.
      - i. Initially contacted
      - ii. Initial interviewed
      - iii. Consented
      - iv. Baseline data collected
  - e. Reasons for non-participation:
    - i. After initial contact and/or initial interview
    - ii. After consent process
    - iii. After initial data collection or throughout the study
    - iv. Until end of study
  - f. Reasons for participating in and completing study

2) Randomization:

- a. Testing effect of randomization process on distribution of demographic, co-morbidity, and other background characteristics
- f. Testing randomization process on their baseline main outcomes
- g. Examining acceptability of the randomization process and its effect

3) Missing data:

- a. Differences in rates of missing data between medication and placebo groups and per time point
- b. Pattern of missing data

4) Retention rate:

- a. Differences in retention between medication and placebo groups
- b. Factors influencing these differences

5) Subjects' satisfaction with:

- a. Study procedures
- b. Study implementation and staffing
- c. Medication delivery methods
- d. Data collection timepoints and outcomes

6) Medication fidelity with:

- a. Delivery methods
- b. Number of successful and failed deliveries
- c. Assessment methods
- d. Timing and method of feedback

7) Study improvement procedures/maintaining documentation of:

- a. Study/protocol development, revision, and modification
- b. Issues and concerns with implementing recruitment strategies
- c. Issues and concerns with accessing, distributing, and tracking of medication and placebo
- d. Issues and concerns with measurements:
  - i. Number of measurements
  - ii. Time requirements of measurements
  - iii. Redundancy among measurements
  - iv. Positive or negative carryover

Sub-study 1c: FoTv vs placebo for use as an adjunct to COVID-19 vaccination.

The primary objectives of this study are to determine whether FoTv, when taken for four consecutive days starting the day of COVID-19 vaccination, is safe and associated with:

- An enhanced peak COVID-19 antibody response
- A reduced rate of post-peak antibody decline
- Reduction in side effects from COVID-19 vaccination

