- Other immunologic (e.g., T-cell mediated) responses

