## Summary

Both mQFPD and FoTv represent potentially lifesaving avenue for the treatment of COVID-19. More specifically, these interventions are likely to be safe, inexpensive, and can be utilized during the early stages of disease when pharmacologic options are limited or unavailable. Further, FoTv may also constitute a means for enhancing the effectiveness of and duration of response to, standard COVID-19 vaccines, as well as for decreasing their side effects. If demonstrated, these properties of FoTv could also potentially contribute to reducing vaccine hesitancy, increasing vaccination rates, and helping to achieve herd immunity.

High quality investigation is urgently required to explore these preventive and therapeutic options for the control of COVID-19.

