## **9. RESEARCH DESIGN AND METHODS**

The following research design applies to each of the following studies:

Sub-study 1a: FoTv vs. placebo for acute COVID-19 patients

Sub-study 1b: QFPD vs. placebo for acute COVID-19 patients

Sub-study 1c: FoTv vs. placebo as an adjunct to COVID-19 vaccination

Sub-studies 1a and 1b of Phase 1 trial will each be 2-arm multicenter double blind randomized placebo controlled clinical trials.

Each of these safety/feasibility sub-studies will be conducted identically with the exception of additional exclusion criteria that will be required for sub-study 1b on account of the presence of herbal components including ephedrine that require these precautions for avoiding herb-drug interactions.

Sub-study 1c will be a single site double blind randomized placebo controlled clinical trial.

This will be a shorter intervention with broader inclusion criteria.

The research design and methods for the larger efficacy trial (Phase 2) will require analysis of these first two feasibility studies, and the final protocol will be submitted as a future amendment.

The primary objective of sub-studies 1a and 1b will be to assess the safety of FoTv or mQFPD, respectively, when used as therapies for acute COVID-19 infection and feasibility of the study protocol.

The primary objectives of sub-study 1c will be to ascertain the safety of FoTv when used as an adjunct to standard COVID vaccination as well as to evaluate its effects on post-vaccine COVID-19 antibody titers and on vaccination-related side effects.

A total of 66 subjects (33 FoTv or mQFPD and 33 placebo) will be enrolled in each of the 1a and 1b sub-studies.

A total of 266 subjects (133 FoTv and 133 placebo) will be enrolled in sub-study 1c.

The study protocol will be implemented and safety, feasibility, clinical, and laboratory data will be collected.

Interested participants will be asked to contact the study team, who will then conduct screening, consenting, and study enrollment. The study will be open to patients who are

- a) Mildly-to-moderately symptomatic and have tested positive for COVID-19 (sub-studies 1a and 1b)
- b) Scheduled for COVID-19 vaccination (sub-study 1c).

See section 11 for recruitment plan.

Once their eligibility has been confirmed, participants will be randomized to one of two groups by the study statistician:

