#### **(2) End-of-Treatment:**

For patients who are not hospitalized, the study phlebotomist will collect their specimens at Day 14 for the following laboratory tests:

- Basic Metabolic Panel
- Complete Blood Count with Differential
- Liver Function Testing

- Prothrombin Time and Partial Thromboplastin Time
- Ferritin
- D-Dimer
- Lactate Dehydrogenase
- C-Reactive Protein
- Troponin
- T-cell differentiation panel
- Salivary or nasal swab samples will be collected for SARS CoV-2 viral load assays
- Plasma, serum, and whole blood will be collected and banked for cytokine, immunological, and metabolomic assays

For subjects who require hospitalization by Day 14, results of the following laboratory tests will be obtained from their hospital records (please note that these tests are routinely conducted as part of COVID-19 treatment and results should be available within subjects' medical records):

- Admission Basic Metabolic Panel,
- Complete Blood Count with Differential, and
- Liver Function Testing.

Please note that medical records will also be reviewed for SARS-CoV-2 viral load, any inflammatory biomarkers (CRP, procalcitonin, IL-6, ferritin, D-dimer, lactate dehydrogenase) as well as markers of myocarditis (troponin, CK-MB) and further lymphocyte differentiation (T-Cell differentiation panel).

Sub-study 1c:

Sample collection will occur at the following time points:

- Single dose vaccine (such as J&J): baseline, day 14, day 28, and 6 months post vaccination
- Two-dose vaccine (such as Pfizer or Moderna): baseline, day 14, two weeks after your second dose, and 6 months post vaccination
- Vaccine booster: baseline, day 3, day 14, and 6 months

For all time points:

The following test will be run to establish values of immunogenicity against SARS CoV-2:

- SARS CoV-2 IgG antibody titer
- Cytokines and T-cell assays

For time points Baseline and Day 14:

The following laboratory assays will be conducted to ascertain FoTv safety:

- Basic Metabolic Panel
- Liver Function Tests

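### Sub-study 1c lists slower post-peak antibody decline as a primary objective, but no planned analysis isolates that decline and no peak visit is named on any of the three sampling schedules

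*Combined protocol and SAP*

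**What the plan says.** In the combined protocol and SAP, Section 6 gives sub-study 1c two separate antibody objectives under its primary objectives: "An enhanced peak COVID-19 antibody response" and "A reduced rate of post-peak antibody decline". Fewer vaccine side effects and "Other immunologic (e.g., T-cell mediated) responses" are in the same list. The Summary of Section 7 gives as a rationale the prospect of "enhancing the effectiveness of and duration of response to, standard COVID-19 vaccines".

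Section 9 restates the 1c aim more loosely. Its opening text and its Statistical Methods subsection refer only to antibody titers, without peak or decline.

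Under Clinical Laboratory Measurements, IgG is sampled on three schedules:
- single-dose vaccine: "baseline, day 14, day 28, and 6 months post vaccination"
- two-dose vaccine: "baseline, day 14, two weeks after your second dose, and 6 months post vaccination"
- booster: baseline, day 3, day 14 and 6 months

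No visit is labelled as the peak. For the two-dose schedule, the text does not say from which dose the 6 months run.

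Statistical Methods And Considerations states: "Wilcoxon-Mann-Whitney rank-sum test will be used to analyze treatment arm versus control arm across study visits and sites". It then adds a mixed regression to confirm the nonparametric results, focused on the treatment by time interaction, with baseline values as individual intercepts and changes across time as slopes. It does not say how time is coded. A Bonferroni correction applies if needed, and the family of tests is not defined.

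**The concern.** A higher peak and a slower fall are different claims, and the plan lists both. A product that raises titers and leaves their decay unchanged would still give a higher 6-month titer. So could one whose titers fall faster from a higher start. If the 6-month comparison or an all-visit interaction is the evidence, the trial could report longer duration of response when decline is no slower than on placebo. The samples needed to separate the two are already in the schedule. What is missing is the definition of the contrast.

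**Working it through.** **Plan's own figure.** No figure is given for the rate of decline. The sample size section cites a program and a medium effect, without power, SD, correlation or contrast, so 266 cannot be reproduced for this objective. Reading medium as d = 0.5 (assumed), a simple two-mean comparison has 98.3% power at 133 per arm and 95.4% at 106.

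**Inputs from the document.** Two-sided 0.05; the three schedules; "A total of 266 subjects (133 FoTv and 133 placebo) will be enrolled in sub-study 1c"; 20% dropout. This gives 266 × 0.8 / 2 ≈ 106 per arm. The sample size section instead puts 53 more on top of 266, so figures for 133 per arm are also shown where available.

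**Assumed inputs (none is in the document).** Log10 SD σ = 0.5 at each visit; equal within-person correlation ρ = 0.5; peak gain g = 0.25 log10 (0.5 SD); 6 months = day 182; dose 2 at day 21 or 28.

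**1. Rank test at 6 months.** The SE of an arm difference in level is √(2 × 0.25 / 106) = 0.0687. The rank test scales the signal by √(3/π) = 0.977.
- Full gain present at 6 months: z = 0.977 × 0.25 / 0.0687 = 3.56, and Φ(3.56 − 1.96) ≈ 94%.
- Half the gain present: z = 0.977 × 0.125 / 0.0687 = 1.78, and Φ(1.78 − 1.96) ≈ 43% (42% in 3,000 simulated trials).

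| Truth | True decline on FoTv | 6-month test favours FoTv, 106 per arm (133) |
|---|---|---|
| Gain at peak, all kept | identical | 94% (98%) |
| No peak gain, +0.25 at 6 months | slower | 94% (97%) |
| Gain at peak, half kept | faster | 42% (52%) |

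Across SD 0.4 to 0.6 at 106 per arm, the first row runs from 84 to 99% and the last from 31 to 60%. A rank test on the change from peak to 6 months does separate the cases. It is significant in 5% (both directions together) when decline is identical, and favours placebo in 42% when half the gain is kept.

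**2. Interaction with linear time.** Let d be each visit day minus the mean day and Sxx = Σd². The arm difference in slope is Σ(d × arm difference)/Sxx, with SE √(2σ²(1−ρ)/(n·Sxx)) = √(0.25/(n·Sxx)). Post-peak decline is set identical (full gain kept) and all 106 per arm are on one schedule. This is a normal approximation.

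| Schedule (days) | Σ(d × difference) | Sxx | z | Significantly positive |
|---|---|---|---|---|
| Single-dose 0/14/28/182, full gain by day 14 | 0.25 × 56 = 14.0 | 21,560 | 1.96 | 50% |
| Same, half the gain at day 14 | 0.25 × 77 = 19.25 | 21,560 | 2.70 | 77% |
| Two-dose 0/14/35/182, half at day 14 | 0.25 × 79.625 = 19.91 | 21,204.75 | 2.81 | 80% |
| Two-dose 0/14/42/182, half at day 14 | 0.25 × 82.25 = 20.56 | 20,923 | 2.93 | 83% |
| Booster 0/3/14/182, gain from day 14 | 0.25 × 96.5 = 24.13 | 23,428.75 | 3.25 | 90% |

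If participants split equally over three schedules (assumed) and each is analysed alone, n ≈ 106/3 ≈ 35. Each z shrinks by √(35/106) = 0.575, and the probabilities become about 20 to 46%. A contrast confined to peak and 6 months would give 5% in both directions together.

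**3. Interaction with categorical time.** For one schedule with four visits the test has 3 df and noncentrality (n/2) × Σ(difference − mean)² / (σ²(1−ρ)). A sustained gain and a decline-only effect both give 53 × 0.0469/0.125 = 19.9 (97% significant). A peak-only effect gives 53 × 0.0625/0.125 = 26.5 (over 99%). All three are detected and none is distinguished.

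**The case against.** The strongest reply is that the mixed model compares change over time between arms and includes individual slopes, so decline is not ignored. That stands. A reader might infer that the plan contains no test bearing on the rate of decline, and the Statistical Methods text does not support this. What remains is that the interaction as written includes the rise from baseline and so does not isolate the fall.

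It is also fair that Section 9 speaks only of antibody titers, so the separate status of decline rests on the Section 6 list. That list is not withdrawn, however. Nor does the plan assign a lead test to antibody titers: it anticipates nonparametric tests and allows a log transformation.

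Three further inferences are tempting and do not hold:
- *The peak visit must be chosen after the data are in.* It can be fixed at any time before unblinding, or defined as each participant's maximum.
- *Balancing the arms on age and BMI causes schedules to be mixed.* Pooling does that, whatever the stratification.
- *A reversed slope is mainly a single-dose risk.* This depends on giving single-dose participants the full gain by day 14 and two-dose participants half. With half for both, the share of the gain at which the single-dose slope changes sign moves from 56% to 39% (two-dose 33 to 36%). The chance of a significantly negative slope with no gain kept falls from 69% to 40%, with all 106 per arm on that schedule.

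The df of a categorical test is not fixed by the plan either. Pooling nominal visits gives six levels, so the 3-df figures only illustrate one schedule.

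**Conclusion.** The concern holds in this form: a listed primary objective, slower post-peak decline, has no planned analysis that isolates it, and no schedule names a peak visit. This is more than missing detail, because the analyses as described can be read as support for slower decline when there is none. Under the stated assumptions that happens in about 94% of trials for the 6-month rank test. For a linear all-visit slope it is about 50 to 90% with everyone on one schedule, or 20 to 46% at 35 per arm.

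The sizes rest on an SD, correlation, gain and timing that the document does not give. The central point does not need them: a difference in late level does not identify a difference in decline. It should be fixed before unblinding.

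**What to change.** Before unblinding:
- Name one peak visit per schedule, for example day 28 (single-dose), two weeks after dose 2 (two-dose) and day 14 (booster). State from which dose the 6 months are counted.
- In the planned mixed model on log10 IgG, make visit categorical and account for vaccine schedule. Pre-specify two contrasts: (1) the arm difference at the peak visit; (2) the arm difference in log10 change from peak to 6 months, per elapsed month.
- Run any rank tests on the same two quantities, stratified by schedule.
- State the Bonferroni family: 0.05/2 = 0.025 each for the two antibody contrasts, or 0.05/4 = 0.0125 each if it covers all four effects listed in Section 6.
- Report the 6-month titer as level only.

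The cost is analysis wording, with no new samples or visits. Some power is lost to alpha sharing. For a decline-only effect of 0.25 log10 with complete data at 106 per arm, the SE of the change is √(4 × 0.25 × 0.5 / 106) = 0.0687 and z = 3.64. Power is Φ(3.64 − 1.96) = 95% at 0.05, Φ(3.64 − 2.24) = 92% at 0.025 and Φ(3.64 − 2.50) = 87% at 0.0125. With SD 0.4 to 0.6 and correlation 0.3 to 0.7 it ranges from 62% to over 99% at 0.025, and from 52% to over 99% at 0.0125. Two visits give only an average rate of decline, not its shape.
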